10.2.5 Assessment of Intensity

The investigator will make an assessment of intensity for each AE reported during the study. An intensity grade will be assigned to each AE. The intensity grading scales used in this study are adapted from the "FDA Guidance for Industry: Toxicity Grading Scale for Healthy Adult and Adolescent Volunteers Enrolled in Preventive Vaccine Clinical Trials, September 2007".

10.2.5.1 Tables for Clinical Abnormalities

10.2.5.1.1 Solicited AR Intensity Grading Scale

Confidential/Proprietary Information Page 68 of 77

Table 10.1: Solicited injection site reactions: terminology, definitions, and intensity scales
- Infants and toddlers aged ≤ 23 months

CRF term (MedDRA lowest level term [LLT])	Injection site tenderness	Injection site erythema	Injection site swelling
Diary card term	Tenderness	Redness	Swelling
Definition	Pain when the injection site is touched or injected limb mobilized	Presence of a redness including the approximate point of needle entry	Swelling at or near the injection site Swelling or edema is caused by a fluid infiltration in tissue or cavity and, depending on the space available for the fluid to disperse, swelling may be either soft (typically) or firm (less typical) to touch and thus can be best described by looking at the size of the swelling
Intensity scale*	Grade 1: CRF and DC: Minor reaction when injection site is touched Grade 2: CRF and DC: Cries or protests when injection site is touched Grade 3: CRF: Cries when injected limb is mobilized, or the movement of the injected limb is reduced DC: Cries when injected limb is moved or the movement of the injected limb is reduced	Grade 1: > 0 to < 25 mm Grade 2: ≥ 25 to < 50 mm Grade 3: ≥ 50 mm	Grade 1: > 0 to < 25 mm Grade 2: ≥ 25 to < 50 mm Grade 3: ≥ 50 mm

^{*} For tenderness, the scale will be provided in the CRF and the intensity will be transcribed from the diary card. For other injection site reactions (erythema and swelling), the classification as Grade 1, 2, or 3 will be applied at the time of statistical analysis; the scale is provided for information purposes only. The actual size of the reaction will be reported in the CRF.

Table 10.2: Solicited systemic reactions: terminology, definitions, and intensity scales – Infants and toddlers aged ≤ 23 months

CRF term (MedDRA lowest level term [LLT])	Fever	Vomiting	Crying abnormal	Drowsiness	Appetite lost	Irritability
Diary card term	Temperature	Vomiting	Abnormal crying	Drowsiness	Loss of appetite	Irritability
Definition	Elevation of temperature to ≥°38.0°C (≥ 100.4°F)	Vomiting does not include spitting up	Inconsolable crying without a determined reason	Reduced interest in surroundings, or increased sleeping	See intensity scale	An excessive response to stimuli: increased fussiness, whining, and fretfulness despite attempts to comfort the infant and despite caregiver responses that would normally be soothing
Intensity scale*	Grade 1: ≥ 38.0°C to ≤ 38.5°C or ≥ 100.4°F to ≤ 101.3°F	Grade 1: CRF and DC: 1 episode per 24 hours	Grade 1: CRF and DC: < 1 hour	Grade 1: CRF and DC: Sleepier than usual or less interested in surroundings	Grade 1: CRF and DC: Eating less than normal	Grade 1: CRF and DC: Easily consolable
	Grade 2: > 38.5°C to ≤ 39.5°C or > 101.3°F to ≤ 103.1°F	Grade 2: CRF and DC: 2– 5 episodes per 24 hours	Grade 2: CRF and DC: 1– 3 hours	Grade 2: CRF and DC: Not interested in surroundings or did not wake up for a feed / meal	Grade 2: CRF and DC: Missed 1 or 2 feeds / meals completely	Grade 2: CRF and DC: Requiring increased attention
	Grade 3: > 39.5°C or > 103.1°F	Grade 3 CRF: ≥ 6 episodes per 24 hours or requiring parenteral hydration DC: at least 6 episodes per 24 hours or requiring intravenous hydration (fluids	Grade 3: CRF and DC: > 3 hours	Grade 3: CRF and DC: Sleeping most of the time or difficult to wake up	Grade 3: CRF and DC: Refuses ≥ 3 feeds / meals or refuses most feeds / meals	Grade 3: CRF: Inconsolable DC: Inconsolable (cannot be comforted)
		hours or requiring intravenous				

^{*} For all reactions (except fever), the scale will be provided in the CRF and the intensity will be transcribed from the diary card. For fever, the body temperature will be recorded, and the classification as Grade 1, 2, or 3 will be assigned at the time of the statistical analysis based on the unit used to measure the temperature and the intensity scale.

Confidential/Proprietary Information Page 70 of 77

Important Notes for the Accurate Assessment of Temperature:

Participants or parents / legally acceptable representatives are to measure body temperature once per day, preferably always at the same time, and using the same standard unit of the considered country (Celsius or Fahrenheit) consistently. The optimal time for measurement is the evening, when body temperature is the highest. Temperature is also to be measured at the time of any apparent fever. The observed daily temperature and the route of measurement are to be recorded in the diary card, and the highest temperature will be recorded by the site in the CRF. The preferred route for this study is axillary.

10.2.5.1.2 Serious and Non-serious Unsolicited AE Intensity Grading Scale

For measurable unsolicited AEs that are part of the list of solicited reactions, the corresponding scale for solicited reactions will be used (see Section 10.2.5.1.1).

All other unsolicited AEs, including SAEs, will be classified according to the following intensity scale:

- Grade 1
 - CRF: A type of adverse event that is usually transient and may require only minimal treatment or therapeutic intervention. The event does not generally interfere with usual activities of daily living.
 - Diary card: No interference with activity.
- Grade 2
 - CRF: A type of adverse event that is usually alleviated with additional therapeutic intervention. The event interferes with usual activities of daily living, causing discomfort but poses no significant or permanent risk of harm to the research participant.
 - Diary card: Some interference with activity.
- Grade 3
 - CRF: A type of adverse event that interrupts usual activities of daily living, or significantly affects clinical status, or may require intensive therapeutic intervention.
 - Diary card: Significant; prevents daily activity.

10.3 APPENDIX: MEASURES FOR A REGIONAL OR NATIONAL EMERGENCY THAT IS DECLARED BY A GOVERNMENTAL AGENCY

A regional or national emergency declared by a governmental agency (eg, public health emergency, natural disaster, pandemic, terrorist attack) may prevent access to the clinical study site.

Contingency procedures are suggested below and in Section 5.5, Section 6.4, Section 8, and Section 10.1.3 for an emergency that prevents access to the study site, to ensure the safety of the participants, to consider continuity of the clinical study conduct, protect study integrity, and assist in maintaining compliance with GCP in Conduct of Clinical Trials Guidance. Sponsor agreement must be obtained prior to the implementation of these procedures for the duration of the emergency.

During the emergency, if the site is unable to adequately follow protocol mandated procedures, alternative treatment outside the clinical study should be proposed, and enrollment administration of study intervention, and blood sampling may be temporarily delayed/halted.

Attempts should be made to perform all assessments in accordance with the approved protocol to the extent possible. In case this is not possible due to a temporary disruption caused by an emergency, focus should be given to assessments necessary to ensure the safety of participants and those important to preserving the main scientific value of the study.

Procedures to be considered in the event of a regional or national emergency declared by a governmental agency:

• If onsite visits are not possible visit windows may be extended for assessment of safety data that cannot be obtained remotely.

Contingencies implemented due to emergency will be documented.

10.4 APPENDIX: RISK-BASED APPROACH

ICH E6-R2 guideline for GCP is introducing the « risk-based approach » concept which permits to focus efforts on what is critical for a study and most specifically on Critical Data and Critical Processes. Critical data and processes are defined for the study with associated risks in the Study Risk Management Plan.

10.5 APPENDIX: ABBREVIATIONS

AE adverse event

AESI adverse event of special interest

AR adverse reaction
BL blood sampling

CDISC Clinical Data Interchange Standards Consortium

CI confidence interval

CIOMS Council for International Organizations of Medical Sciences

CRF case report form

D day

DC diary card

DNA deoxyribonucleic acid

EU European Union FAS full analysis set

GCP Good Clinical Practice

GMC geometric mean concentration

GMT geometric mean titer

GPV Global Pharmacovigilance

hSBA serum bactericidal assay using human complement

IB Investigator's Brochure ICF informed consent form

ICH International Council for Harmonisation

IEC Independent Ethics Committees

IM intramuscular

IMD invasive meningococcal diseaseIMP investigational medicinal product

IRB Institutional Review Boards

MCV4 quadrivalent meningococcal conjugate vaccine
MedDRA Medical Dictionary for Regulatory Activities

mL milliliter

NIMP non-investigational medicinal product
PIAF Protocol Investigator Agreement Form

PPAS per-protocol analysis set

PV pharmacovigilance

RCDC reverse cumulative distribution curve

RMO Responsible Medical Officer

rSBA serum bactericidal antibody assay using baby rabbit complemen

SAE serious adverse event SafAS safety analysis set

SAP statistical analysis plan SoA schedule of activities

SUSARs suspected unexpected serious adverse reactions

TBD to be determined
TC telephone call
TT tetanus toxoid
US United States

Table 4.1: Solicited injection site reactions: terminology, definitions, and intensity scales –	
Infants and toddlers aged ≤ 23 months	19
Table 4.2: Solicited systemic reactions: terminology, definitions, and intensity scales – Infants	
and toddlers aged ≤ 23 months	

List of Figures

1 Overall Design

[figure not shown]
The design of the study is summarized in Table 1.1.

Table 1.1: Overall Design

Type of design	Open-label, single-group, multi-center
Phase	IV
Control method	Un-controlled
Study population	Healthy toddlers aged 12 months to 23 months
Level and method of blinding	Open-label
Study intervention assignment method	No randomization
Number of participants	A total of approximately 180 participants (minimum of 30 evaluable participants from the low - enrolling of the 2 priming vaccines) are expected to be enrolled with the aim to obtain a total of 150 evaluable participants.
Intervention groups	All eligible participants (12 – 23-month-old toddlers who had received at least one of two priming doses of either Nimenrix® or Menveo® vaccine during infancy as part of their recommended immunization, before 12 months of age) will be assigned in an open-label design to receive a single booster dose of the MenACYW conjugate vaccine with an interval of at least 2 months after the last vaccination with Nimenrix® or Menveo®, as an intramuscular (IM) injection at D01.
Total duration of study participation	The duration of each participation will be approximately 1 month for each participant
Countries	Argentina
Use of an Independent Data Monitoring Committee, Dose Escalation Committee, or similar review group	No

The study design of MEQ00086 study is presented in Figure 1.1.

Figure 1.1: Graphical study design

BL: blood sample

BL0001 (pre-vaccination) and BL0002 for immunogenicity assessments

D: day; TC: telephone call;

D09 TC1: Day 09 safety follow up

: Vaccination

The schedule of activities are given in Table 1.2

Table 1.2: Schedule of activities

Phase IV Study, 2 Visits, 1 Vaccination, 2 Blood Samples, ~1 Month Duration Per Participant

Visit/Contact	Collection of information in the CRF	Visit 1	TC1§	Visit 2**
Study timelines (days)		D01	D09	D31
Time windows (days)		NA	[+2 D]	[+14 D]
Visit procedures:				
Informed consent	X	X		
Inclusion/exclusion criteria	X	X		
Collection of demographic data	X	X		
Collection of Medical history	X Significant Medical History	X		
Collection of vaccination history	X	X		
Physical examination		X		X
Pre-vaccination temperature		X		
Review of temporary contraindications for blood sampling*	Х	X		X
Allocation of participant number	X	X		
Blood sampling (BL)† [5 mL]	X	BL0001 Pre-vac		BL0002
Vaccination (vac)	X	X		
Immediate surveillance (30 min)	X	X		
Diary card provided		X		
Collection of solicited injection site and systemic reactions	X	X	X	
Collection of unsolicited adverse events (AEs)	X	X	X	X
Diary card collected				X
Collection of concomitant medications	X Reportable concomitant medication	X	X	X
Collection of SAEs, including adverse events of special interest (AESIs)	X	To be reported at any time during the study from D01 to D31 (+14 days) after study vaccination		
End of Active Phase participation record‡	X			X

AESI: Adverse Events of Special Interest; CRF: case report form; SAE: Serious Adverse Events

^{*} Should a participant receive oral or injectable antibiotic therapy within 3 days prior to each blood draw, the Investigator will postpone that blood draw until it has been 3 days since the participant last received oral or injectable antibiotic therapy. Postponement is still to be within the timeframe for blood draw (30 to 44 days after vaccination at D01). If postponement will

result in the sample collection falling outside of the appropriate timeframe, the blood sample should be collected without postponement, and it should be documented appropriately that the sample was taken less than 3 days after stopping antibiotic treatment.

- † Blood sample at D01 will be drawn before administration of the vaccine
- ‡In case of participant discontinuation at a visit, the entire visit will be completed. Active Phase is from Visit 1 to Visit 2 completion.
- § The Investigator or an authorized designee will remind the parents, guardians, or legally acceptable representatives to bring back the diary card (DC) at the next visit and will answer any questions. If D09 falls on a weekend or holiday, the telephone call may be made on the following business day. During this telephone call, the staff will find out whether the participant experienced any SAEs (including AESIs) not yet reported and will remind the participant's parent/guardian to continue using the diary card, to bring the diary card to the study center at the next visit and confirm the date and time of the next visit.
- **The Investigator or an authorized designee will interview the parents, guardians, or legally acceptable representatives to collect the information recorded in the DC and will attempt to clarify anything that is incomplete or unclear.

2 Objectives and Endpoints

The study objectives and the corresponding endpoints are described in Table 2.1.

Table 2.1: Objectives and endpoints

	Objectives		Endpoints		
Immunogenicity			Immunogenicity		
1)	To describe the immune response to a booster	1)	hSBA antibody titers $\geq 1:8$ (seroprotection)		
	dose of MenQuadfi® as measured by the serum		against meningococcal serogroups A, C, W and		
	bactericidal assay using human complement		Y at D31 (+14 days) after booster vaccination		
	(hSBA) in toddlers aged 12-23 months, who had		with MenQuadfi®		
	been primed with at least 1 dose of another	2)	At Day (D)01 (baseline) before vaccination and		
	MCV4 vaccine during infancy		at D31 [+14 days] after the administration of a		
2)	To describe the antibody responses to		booster dose of MenQuadfi® the following will		
	meningococcal serogroups A, C, W, and Y		be assessed for meningococcal serogroups A, C,		
	before and 1 month after a booster dose of		W and Y as measured by hSBA:		
	MenQuadfi® as measured by hSBA and rSBA in	•	Antibody titers against meningococcal		
	toddlers 12-23 months of age who had been		serogroups A, C, W, and Y		
	primed with at least 1 dose of another MCV4	•	Antibody titers $\geq 1:4$ and $\geq 1:8$		
	vaccine during infancy	•	≥ 4-fold rise from pre-vaccination to post-		
3)	To describe the antibody responses to		vaccination		
	meningococcal serogroups A, C, W, and Y	•	Vaccine seroresponse, defined as follows:		
	before and 1 month after a booster dose of	•	For a participant with a pre-vaccination titer		
	MenQuadfi® as measured by hSBA and rSBA in		< 1:8, a post-vaccination titer ≥ 1:16		
	- 8	•	For a participant with a pre-vaccination titer		
	primed with 2 doses of another MCV4 vaccine		≥ 1:8, a post-vaccination titer at least 4-fold		
	during infancy	١	greater that the pre-vaccination titer		
4)		At	Day (D)01 (baseline) before vaccination and at		
	meningococcal serogroups A, C, W, and Y		D31 [+14 days] after the administration of a		
	before and 1 month after a booster dose of		booster dose of MenQuadfi® the following will		
	MenQuadfi® as measured by hSBA and rSBA in		be assessed for meningococcal serogroups A, C,		
	toddlers 12-23 months of age who had been		W and Y as measured by rSBA:		
	primed with 1 dose of another MCV4 vaccine	•	Antibody titers against meningococcal		
5)	during infancy		serogroups A, C, W, and Y		
5)	To describe the antibody responses to tetanus toxoid before and 1 month after a booster dose	•	Antibody titers $\geq 1:8$ and $\geq 1:128$		
	of MenQuadfi® in toddlers 12-23 months of age	•	≥ 4-fold rise from pre-vaccination to post-vaccination		
	who had been primed with at least 1 dose of		Vaccine seroresponse defined as follows:		
	another MCV4 vaccine during infancy		For a participant with a pre-vaccination titer		
	another fire v4 vaccine during infancy		< 1:8, a post-vaccination titer \ge 1:32		
			For a participant with a pre-vaccination titer		
			≥ 1:8, a post-vaccination titer at least 4-fold		
			greater that the pre-vaccination titer		
		3)	Same endpoints as described for endpoint #2		
		4)	Same endpoints as described for endpoint #2		
		5)	Antibody concentrations against tetanus toxoid		
			at D01 (baseline) and at D31 (+14 days) after		
			the administration of a booster dose of		
			MenQuadfi®		

Safety	Safety	
To describe the safety profile of a booster dose of MenQuadfi® administered to toddlers 12-23 months of age who had been primed with at least 1 dose of another MCV4 vaccine during infancy	 Presence of any unsolicited systemic adverse events (AEs) reported in the 30 minutes after vaccination. Presence of solicited (pre-listed in the participant's diary card [DC] and case report form [CRF]) injection site reactions up to 7 days after vaccination. Presence of solicited systemic reactions (pre-listed in the participant's DC and CRF) up to 7 days after vaccination. Presence of unsolicited AEs up to 30 days after vaccination. Presence of serious adverse events (SAEs) [including AESIs], throughout the trial from Visit 1 to 30 days after study vaccination. Depending on the items, the endpoints recorded or derived could include: Nature (Medical Dictionary for Regulatory Activities [MedDRA] preferred term), time of onset, duration/number of days of occurrence, intensity, relationship to the vaccine, whether the AE led to early termination from the study, outcome, and seriousness criterion 	

3 Statistical Considerations

3.1 Statistical Hypotheses

No hypotheses will be tested. The analyses will be descriptive.

3.2 Sample Size Determination

There are no statistically powered hypotheses in this study thus no formal sample size computation. All analyses will be descriptive.

The sample size was set to approximatively 180 participants (minimum of 30 evaluable participants from the low-enrolling of the 2 priming vaccines) to have at least 150 evaluable participants assuming a drop-out rate of approximatively 15%.

In terms of immunogenicity for any of the 4 serogroups, considering a sample size of 150 evaluable participants, the expected precision of the 95% CI using the Exact binomial method will be as follow:

Seroprotection rates (titer >= 1:8)	Precision*
85%	13.77
90%	11.62
95%	8.96
100%	2.88

^{*}Difference between the upper and lower bounds of the 95%CI

In terms of safety, the planned sample size will allow for identification of common AEs. One hundred and fifty evaluable participants will allow with 95% probability, the detection of an AE occurring with a frequency of 2% or more, using the rule of threes.

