9.5 SAMPLE SIZE DETERMINATION

There are no statistically powered hypotheses in this study thus no formal sample size computation. All analyses will be descriptive.

The sample size was set to approximatively 180 participants (minimum of 30 evaluable participants from the low - enrolling of the 2 priming vaccines) to have at least 150 evaluable participants assuming a drop-out rate of approximatively 15%.

In terms of immunogenicity for any of the 4 serogroups, considering a sample size of 150 evaluable subjects, the expected precision of the 95% CI using the Exact binomial method will be as follow:

Seroprotection rates (titer >= 1:8)	Precision*
85%	13.77
90%	11.62
95%	8.96
100%	2.88

^{*}Difference between the upper and lower bounds of the 95%CI

In terms of safety, the planned sample size will allow for identification of common AEs. One hundred and fifty evaluable subjects will allow with 95% probability, the detection of an AE occurring with a frequency of 2% or more, using the rule of threes.

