3.4 Statistical Analyses

3.4.1 General Considerations

Immunogenicity parameters will be analyzed in specified analysis sets (PPAS and FAS) in the overall population, as well as by primed vaccine groups. Safety analysis will be performed on the SafAS.

The statistical analyses will be performed under the responsibility of the Sponsor's Biostatistics platform using SAS® Version 9.4 or later.

For descriptive purposes, the following statistics will be presented:

Table 3.1: Descriptive statistics produced

Disposition and follow-	Categorical data	Number of participants.		
up description		Percentage of participants.		
	Continuous data	Mean, standard deviation, quartiles, minimum and		
		maximum.		
Baseline characteristics	Categorical data	Number of participants.		
		Percentage of participants.		
	Continuous data	Mean, standard deviation, quartiles, minimum and		
		maximum.		
Clinical safety results	Categorical data	Solicited: Number and percentage (95% CIs for		
		main endpoints) of participants.		
		Unsolicited: Number and percentage (95% CIs for		
		main endpoints) of participants and number of		
		events.		
Immunogenicity	Categorical data	Number and percentage (95% CIs for main		
results	(seroprotection,	endpoints) of participants		
	seroconversion, cutoff)			
	Continuous data (titer /	Log10: Mean and standard deviation. Anti-Log10		
	data†)	(work on Log10 distribution, and anti-Log10		
		applied): Geometric mean, 95% CI of the geometric		
		mean, quartiles, minimum, and maximum. Graphical		
		representation by Reverse Cumulative Distribution		
		Curve (RCDC).		

The confidence interval (CI) for the single proportion will be calculated using the exact binomial method (Clopper-Pearson method, quoted by Newcombe (1), i.e., using the inverse of the beta integral with SAS®.

For immunogenicity results, assuming that Log10 transformation of the titers / data follows a normal distribution, at first, the mean and the 95% CI will be calculated on Log10 (titers / data) using the usual calculation for normal distribution (using Student's t distribution with n-1 degree of freedom), then antilog transformations will be applied to the results of calculations, in order to provide geometric means (GMs) and their 95% CI.

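### The sample-size precision table is labelled 95% exact CI at n = 150, but all four widths are those of a 97.5% interval

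*SAP*

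**What the plan says.** The study is descriptive. SAP section 3.2 states: "There are no statistically powered hypotheses in this study thus no formal sample size computation". In place of a power calculation, it gives the confidence-interval width expected at four assumed seroprotection rates, "considering a sample size of 150 evaluable participants, the expected precision of the 95% CI using the Exact binomial method will be as follow". Protocol section 9.5 has the same sentence, with only the word for participants changed: "considering a sample size of 150 evaluable subjects, the expected precision of the 95% CI using the Exact binomial method will be as follow". The two tables are identical:

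| Assumed seroprotection rate | Printed precision (points) |
|---|---|
| 85% | 13.77 |
| 90% | 11.62 |
| 95% | 8.96 |
| 100% | 2.88 |

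The footnote defines precision as "Difference between the upper and lower bounds of the 95%CI", so these are full widths. The method is fixed in SAP section 3.4.1: "The confidence interval (CI) for the single proportion will be calculated using the exact binomial method (Clopper-Pearson method", obtained from the inverse beta function. Protocol section 9.3.2 and SAP section 3.4.2 likewise specify 95% exact intervals for percentages.

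**The concern.** Sample size, method, confidence level and width definition are all stated, so each row has a definite value that can be checked. The 90% and 100% rows correspond to whole counts out of 150 and need no rounding choice, yet both miss the 95% value.

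No hypothesis is tested (Protocol 9.1, SAP 3.1), so this table is all the plan offers to show what 150 evaluable participants provide for immunogenicity. If it describes a different interval from the one to be reported, any comparison of achieved with planned precision uses the wrong benchmark. For example, an observed 95% width of about 12 points at 85% seroprotection would look better than planned, although it is only what n = 150 should give.

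**Working it through.** **Inputs.** n = 150, rates of 85%, 90%, 95% and 100%, two-sided 95% level, width = upper minus lower bound (SAP 3.2, Protocol 9.5); Clopper-Pearson limits (SAP 3.4.1).

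**Formula.** For x responders out of n and total alpha α:

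- lower = Beta quantile at α/2 with parameters (x, n − x + 1)
- upper = Beta quantile at 1 − α/2 with parameters (x + 1, n − x), set to 1 when x = n

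**Counts.** 90% and 100% of 150 are 135 and 150. 85% and 95% are 127.5 and 142.5, so a rounding choice is needed. Rounding down gives 127 and 142.

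**Results at n = 150.**

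| x/150 | Printed width | 95% interval (α = 0.05) | 95% width | 97.5% interval (α = 0.025) | 97.5% width |
|---|---|---|---|---|---|
| 127 | 13.77 | 77.89 to 90.02 | 12.14 | 76.89 to 90.66 | 13.770 |
| 135 | 11.62 | 84.04 to 94.29 | 10.25 | 83.14 to 94.77 | 11.621 |
| 142 | 8.96 | 89.76 to 97.67 | 7.91 | 89.00 to 97.95 | 8.959 |
| 150 | 2.88 | 97.57 to 100 | 2.43 | 97.12 to 100 | 2.879 |

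No row matches at 95%. All four match at 97.5%.

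**The 100% row by hand.** With x = n the lower limit is (α/2)^(1/n).

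- α = 0.05: 0.025^(1/150) = 0.9757, width 2.43.
- α = 0.025: 0.0125^(1/150) = 0.9712, width 2.88.
- Solving for the alpha behind the printed value: 2 × (1 − 0.0288)^150 = 0.02496, which is 0.025 within rounding.

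**Other explanations tried.**

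- *Rounding up.* 128 and 143 give 95% widths of 11.93 and 7.48, further from the printed values.
- *A different n at 95%.* The four rows imply n of about 116, 118.5, 114 and 126, so no single n fits.
- *A different 95% method at n = 150.* At the nominal rates, Wilson gives 11.42, 9.69, 7.25 and 2.50; the normal approximation gives 11.43, 9.60, 6.98 and 0. Adding a continuity correction to the latter gives 12.10, 10.27, 7.64 and 0.67. None matches.
- *A different confidence level.* 90%, 98% and 99% exact intervals do not match either.

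**Size of the error (rounding down).**

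- 85%: 13.77 − 12.14 = 1.63 points; 13.77/12.14 = 1.13
- 90%: 11.62 − 10.25 = 1.37 points; 11.62/10.25 = 1.13
- 95%: 8.96 − 7.91 = 1.05 points; 8.96/7.91 = 1.13
- 100%: 2.88 − 2.43 = 0.45 points; 2.88/2.43 = 1.19

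**Rest of the section.** Dropout: 150/0.85 = 176.5, consistent with about 180 enrolled. Safety: 1 − 0.98^150 = 0.952, consistent with the stated 95% chance of detecting an event with 2% frequency. Both statements stand.

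**The case against.** The strongest reply is that nothing depends on these four numbers. The error is conservative, since the true 95% intervals are narrower than printed. The documents set no target width, and no decision rule uses the table. They present 150 as a chosen number and then show its precision, so it was not solved from the table. All of this is correct, and it limits the importance of the error, but it does not make the printed values right under their own label.

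Second, SAP section 5 reports that recruitment stopped before 180, so the table had become a historical planning statement. The documents do not give the final evaluable number. If it is below 150, the corrected widths will not describe the achieved precision either. That is true, but a planned benchmark that readers will set against the results should still be correct.

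Third, the correct width is not unique in two rows. With 128 and 143 in place of 127 and 142, the 95% widths are 11.93 and 7.48, and the overstatement is 1.84 and 1.48 points (15% and 20%). This stands and is why the counts should be stated. The 90% and 100% rows are unaffected and settle the matter alone.

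Finally, nothing in the documents suggests that the analysis programs share the slip. That also stands: checking them is a precaution.

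**Conclusion.** The concern holds: the table is wrong as written in both documents. Its values are 97.5% Clopper-Pearson widths at n = 150, labelled as 95%. They overstate the 95% widths by 0.45 to 1.63 points (13% to 19%) at counts of 127, 135, 142 and 150. At 100% seroprotection the 95% lower bound is 97.57%, whereas the printed width implies 97.12%.

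The result rests only on the stated n, method, level and width definition, plus rounding down in the 85% and 95% rows, which is the rounding that reproduces the printed values. The probable cause is that 0.025 was entered as total alpha and then halved again. That is inference; the documents do not say.

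The consequence is modest. Precision is understated, the choice of 150 evaluable participants stands, and the analysis sections still specify 95% intervals. It is a plain correction to the planning figures and does not threaten the study's conclusions.

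**What to change.** In Protocol section 9.5 and SAP section 3.2, replace the precision column with 12.14, 10.25, 7.91 and 2.43, and state the counts behind it (127, 135, 142 and 150 of 150). If the protocol is no longer being amended, correct the SAP and record the protocol error in SAP section 5 or in an erratum.

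As a precaution, confirm that the SAS programs producing the reported exact intervals use a total alpha of 0.05.

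The cost is four numbers in two documents and a brief program check. No extra participants or data are needed.
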